# 6.4.3 Removal of Subjects from the Trial or Study Drug

Subjects will be free to withdraw at any time for any reason, or they may be withdrawn if necessary, to protect their health and safety or the integrity of the study data. A subject will be removed from participation in the study if any of the following occur:

- Any clinical adverse event (AE), laboratory abnormality, intercurrent illness, or other medical condition or situation arises such that in the judgment of the PI continued participation in the study would not be in the best interest of the subject
- A protocol violation/deviation occurs that might compromise the integrity of the data, compliance, or subject safety
- Informed consent is withdrawn
- Subject is lost to follow-up

# 6.4.4 Handling Withdrawals

If a subject is withdrawn prematurely from the study after receiving Nu-3, the reason for withdrawal is to be documented in the source document and in the CRF. If the withdrawal of a subject is due to an AE, the subject will be followed until resolution/stabilization of the adverse event.

In the case of a subject prematurely withdrawing from the study, the following procedures and/or evaluations will be performed if possible at the time of withdrawal or as soon thereafter as possible (i.e. study subject withdraws at time of visit and consents to the procedures or consents to come in for a visit and the procedures)

- Photo documentation of ulcer site using the Aranz Medical SilhouetteTM system.
- Collection of a sample for microbiological assessment

# • Assessment of adverse events

In the event a subject is lost to follow-up, the site staff must make reasonable attempts to contact the subject. A minimum of two documented phone calls followed by a certified mailed letter is considered reasonable. The measures taken to follow up must be documented.

Administrative withdrawals will be replaced in order to achieve the objective of 10 subjects per cohort who receive a complete treatment regime. Subjects withdrawn from the study due to an AE/SAE related to the study drug will not be replaced.

# 7 STATISTICAL CONSIDERATIONS

# 7.1 Study Hypothesis

Study Hypothesis – Bisphosphocin Nu-3 solution applied topically to a chronic infected diabetic ulcer will be safe and well tolerated in subjects suffering from diabetes mellitus. In addition, the Nu-3 MAD Arm subjects may show improvement in the ulcer appearance, reduction in size, and improvement in both the DUSS score and DFI Wound Score.

The study hypothesis will be judged by the following two study objectives:

- Primary objective: To assess the safety and tolerability of escalating single and multiple doses of Nu-3, a novel antimicrobial of the bisphosphocin class, topically to an open wound/diabetic ulcer
- Secondary objectives: To assess clinical response of subjects of the ascending multiple dose arm of Nu-3 applied topically to an open wound/diabetic ulcer to determine clinical and microbiological response.

# 7.2 Sample Size Considerations

The number of treated subjects is based on the desire to gain preliminary safety, tolerability and efficacy information to support future work, while exposing a minimal number of subjects to the study procedures and medication. Inferential statistical testing is not the primary intent of the study, therefore, no formal sample size calculation was considered. Ten subjects per Cohort (1, 2, and 3), for a total not to exceed 30, is considered sufficient to show clinical significance for safety and preliminary efficacy analysis. The sample sizes for this study were set based on the trial design for dose escalation and safety evaluation requirements and not for statistical analysis.

# 7.3 Planned Interim Analysis

There will be an interim analysis to review safety data on each cohort of subjects when all members of a cohort complete Visit 4 (7-Day MAD Follow Up). In addition, an interim analysis will be conducted after the first 5 subjects of Cohort 2 and 3 complete Visit 4 (7-Day MAD Follow Up). The interim analysis will be performed by the Safety Monitoring Committee (SMC) which will be composed of three physicians and may include one infectious disease specialist, one diabetologist, and one orthopedic surgeon. The SMC will communicate by email or teleconference on at least 3 occasions during the study and more frequently if necessary.

No formal statistical interim analyses are planned for this Phase I/IIa study since it is primarily focused on evaluating safety and tolerability. Interim safety data on each cohort will be provided to the SMC when all members of a cohort have reached Day 3. The SMC will decide if the study can proceed to the next dose cohort (majority vote). The SMC will also determine if the study may proceed after receiving a report about a study related Grade 3 or 4 adverse event

(majority vote). The Chairman of the SMC will share their findings and recommendations with Lakewood Amedex and Principal Investigators.

# 7.3.1 Safety Review

Subjects will be monitored closely for the occurrence of study related adverse events during their 24-hr admission in the SAD Arm and for up to 7 days following their last Nu-3 treatment in the study. If any grade 3 or 4 adverse events occur and the event is judged to be probably or definitely related to having received the Nu-3, the study will be immediately suspended by the Principal Investigator pending review of all safety data. Adverse events determined to be related to the study drug will be reported to the SMC, Lakewood-Amedex, and second PI within 24 hours of notification of its occurrence. No additional subjects will receive Nu-3 depending on the joint decision of the SMC, Principal Investigator, and Lakewood Amedex Project Coordinator and CMO as to whether further doses can be given or the entire study should be terminated. In addition, the SMC will review all interim safety data prior to the next cohort beginning treatment. At each review, the SMC will determine whether the study may proceed to the next dose cohort (majority vote).

# 7.4 Statistical Analysis Overview

This study is designed to evaluate the safety, tolerability, and preliminary efficacy of a minimum of three dose levels of Nu-3 relative to placebo. Data summaries will be presented in order to assess the safety of Nu-3 and each Nu-3 dose group will be compared with placebo to determine the presence or absence of a treatment effect. Evaluation across all dose levels of Nu-3 will be conducted to determine if there is evidence of a dose response to any treatment effect noted. All subjects treated with placebo from all cohorts will be combined for any analysis. Evaluations will also be conducted within each subject over time to assess the rate of change (if any) in study outcome measures over the full course of the study treatment and follow-up periods. Inferential statistical testing is not the primary interest of this study.

All subjects receiving any amount of study treatment will be evaluated for safety, tolerability, and efficacy. An "intent to treat" approach will be followed in all data summaries, using all available data in the summaries and analysis for an assessment of safety and tolerability while an "as treated" approach will be used for microbiological and clinical wound assessment data summaries and reports.

All descriptive summaries and analyses will be presented in tabular and/or graphical form from all subjects as appropriate. These summaries and analysis will be described in detail in the Statistical Analysis Plan (SAP) which will be produced prior to breaking the study blind. All statistical summaries and analysis will be conducted using SAS®.

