#### **Statistical Analysis**

Summary tables (descriptive statistics and/or frequency tables) will be provided for all baseline variables, efficacy variables, and safety variables. Continuous variables will be described by descriptive statistics (n, mean, standard deviation, minimum, maximum, median, 95% confidence limits for the mean).

Frequency tables will be used to report adverse event frequency by system organ class (SOC), preferred term (PT), severity, and relationship to test article. All subjects receiving the test article will be included in the safety analyses.

Safety data including laboratory evaluations and vital signs assessments are summarized by dose group and time point of collection. Descriptive statistics are calculated for quantitative safety data, and frequency counts are compiled for classification of qualitative safety data. In addition, a mean change from baseline table is provided for vital signs and a shift table describing out of normal range shifts is provided for clinical laboratory results. Changes in physical examinations are described in the text of the final report.

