#### **4. GENERAL ANALYSIS CONSIDERATIONS**

The statistical analyses will be reported using summary tables and data listings. For all efficacy parameters, a comparison will be made of each active treatment group versus placebo using the appropriate statistical test. Unless otherwise indicated, all statistical tests will be two-sided and differences will be considered statistically significant if the associated p-value is less than 0.05. Continuous variables will be summarized with means, standard deviations (SD), medians, minimums, and maximums. Categorical variables will be summarized by counts and by percentage of subjects in corresponding categories. All data will be summarized by dose group (cohort), with all placebo subjects combined into one placebo arm.

Individual subject data obtained from the electronic data capture system, study lab, and any derived data will be presented by cohort for each subject in data listings.

The analyses described in this plan are considered *a priori*, in that they have been defined prior to database lock for individual subjects. Any analyses performed subsequent to database lock will be considered post-hoc and exploratory. Post-hoc analyses will be identified in the CSR.

All analyses and tabulations will be performed using SAS® Version 9.4 or higher on a Windows platform. Tables and listings will be presented in PDF format. Upon completion, all SAS® programs will be validated by an independent programmer. In addition, all program output will undergo a senior level statistical review. The validation process will be used to confirm that statistically valid methods have been implemented and that all data manipulations and calculations are accurate. Checks will be made to ensure accuracy, consistency with this plan, consistency within tables, and consistency between tables and corresponding data listings. Upon completion of validation and quality review procedures, all documentation will be collected and filed by the project statistician or designee.

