## **8.2 Analysis of Efficacy Endpoints**

For each dose group, the proportion of subjects with a normal culture at the end of the MAD portion of the study will be compared to the proportion of subjects with a normal culture at the end of the MAD portion of the study for the combined placebo group using a Fisher's exact test. A subject with a normal culture at this time will be considered a success. Any subject with a missing value at the end of the MAD portion of the study will not be included in the analysis. A p-value less than 0.05 will be considered statistically significant and a p-value less than 0.0167, employing a Bonferroni correction for multiple comparisons, will be considered highly conclusive.

For continuous efficacy endpoints, data will be summarized descriptively at and a comparison using the Wilcoxon Rank Sum test between each of dose groups and the combined placebo group will be performed at each visit. For these endpoints, no imputation for missing values will be performed.

For categorical endpoints, a Fisher's exact test will be performed in a similar manner. Subjects missing a value for a secondary endpoint will be considered a failure (counted in the denominator) for that endpoint.

For all tests, a p-value less than 0.05 will be considered statistically significant and a p-value less than 0.0167, employing a Bonferroni correction for multiple comparisons, will be considered highly conclusive. Analysis for each secondary endpoint will be performed on the ITT population and the PP population.

Ulcer measurements and percentage of area reduction will be summarized descriptively by visit and statistical testing using a Wilcoxon Rank Sum test between each dose group and the combined placebo group. For all tests, a p-value less than 0.05 will be considered statistically significant. Analysis for each additional endpoint will be performed on the ITT population and the PP population.

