## **10. SAMPLE SIZE AND POWER**

This is a pilot dose-ranging study. No sample size calculations were conducted.

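### SAP 8.2 judges each dose against at most six pooled placebo subjects by p-value labels and specifies no between-group estimate or confidence interval

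*Protocol*

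**What the plan says.** SAP section 3 plans three cohorts of ten, randomized 4:1, and section 4 pools all placebo subjects into one arm. Section 4 also calls for a two-sided test of each active group against placebo on every efficacy parameter, at 0.05. Section 8.2 uses Fisher's exact test for normal culture and the other categorical endpoints, and the Wilcoxon rank-sum test for continuous ones. It then adds a second tier: "a p-value less than 0.0167, employing a Bonferroni correction for multiple comparisons, will be considered highly conclusive".

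On reporting, SAP section 4 says: "Continuous variables will be summarized with means, standard deviations (SD), medians, minimums, and maximums". Categorical data get counts and percentages, by dose group. The supplied text of sections 4 and 8.2 asks for no difference between groups and no interval.

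The protocol file holds a five-cohort protocol and two three-cohort protocol texts. Section 7.4 of both three-cohort texts says "each Nu-3 dose group will be compared with placebo to determine the presence or absence of a treatment effect", and section 7.2 says ten per cohort "is considered sufficient to show clinical significance for safety and preliminary efficacy analysis". The same sections hold back: "Inferential statistical testing is not the primary interest of this study", and the sizes were "set based on the trial design for dose escalation and safety evaluation requirements and not for statistical analysis". The five-cohort text contains neither the presence-or-absence wording nor the sufficiency wording. Its synopsis lists "95% confidence limits for the mean" among the descriptive statistics, which the SAP does not carry over.

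**The concern.** The SAP's secondary objectives include supporting the choice of dose range for later studies. That choice depends on how large each dose's effect might be and how uncertain it is. A significance label at 8 against 6 gives neither. If labels are the only between-group result, an active concentration that misses p<0.05 can look the same in the report as an inactive one, and the reader has no interval showing which effects remain possible.

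**Working it through.** **Inputs from the documents.** 8 Nu-3 and 2 placebo per cohort; three cohorts (SAP section 3); placebo pooled (SAP section 4), so 3 × 2 = 6. For culture, SAP 8.2 drops subjects with a missing value, so 8 v 6 is the maximum. Tests are two-sided at 0.05, with the second tier at 0.0167.

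**The plan's own figure.** 0.05 / 3 = 0.0167, which reproduces the second-tier cut-off. There is no power figure to reproduce: "No sample size calculations were conducted". No response rates or SDs are stated, so those below are assumptions.

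**1. What Fisher's test can declare at 8 v 6.** For p<0.05 in Nu-3's favour the smallest results are:

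| Placebo successes | Nu-3 successes needed | p |
|---|---|---|
| 0/6 | 5/8 | 0.031 |
| 1/6 | 7/8 | 0.026 |
| 2/6 | 8/8 | 0.015 |
| 3/6 or more | none | 8/8 v 3/6 gives 0.055 |

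The last row by hand: with 11 successes among 14, P(8/8, 3/6) = C(8,8)·C(6,3) / C(14,11) = 20/364 = 0.055, and no other table is as unlikely.

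**2. Power.** Power = Σ over a and b of Bin(a; 8, p1) · Bin(b; 6, p0), taken over tables with Fisher p below the cut-off.

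| Placebo v Nu-3 (assumed) | 8 v 6, 0.05 | 8 v 6, 0.0167 | 8 v 10, 0.05 |
|---|---|---|---|
| 20% v 60% | 20% | 9% | 30% |
| 20% v 70% | 33% | 18% | 45% |
| 20% v 80% | 49% | 32% | 63% |
| 10% v 70% | 52% | 32% | 71% |
| 30% v 70% | 19% | 10% | 27% |
| 0% v 70% | 81% | 55% | 94% |

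The 81% can be checked directly: with no placebo successes, significance needs 5 or more of 8, and P(Bin(8, 0.7) ≥ 5) = 0.806. The 8 v 10 column is the five-cohort design.

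**3. Continuous endpoints.** Simulated normal shifts with exact Wilcoxon p-values at 8 v 6 and 0.05 give power of 12% for 0.5 SD, 36% for 1.0 SD, 67% for 1.5 SD and 80% for 1.75 SD. The 95% half-width for a mean difference is t(12) × √(1/8 + 1/6) = 2.179 × 0.540 = 1.18 SD.

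**4. What a non-significant table can hide.** Take 5/8 v 1/6.
- Fisher: six successes in all; tables no more likely than the observed one have weights 336 + 28 + 48 + 1 = 413 out of C(14,6) = 3003, so p = 0.14.
- Difference: 0.625 − 0.167 = 0.458.
- Wilson limits: 0.306 to 0.863 for 5/8; 0.030 to 0.564 for 1/6.
- Newcombe lower limit: 0.458 − √[(0.625 − 0.306)² + (0.564 − 0.167)²] = −0.05.
- Newcombe upper limit: 0.458 + √[(0.863 − 0.625)² + (0.167 − 0.030)²] = 0.73.

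The p-value carries no label, while the interval runs from a small deficit to a 73-point benefit. Even 4/8 v 3/6, with a difference of zero, has limits of −42 to 42 points.

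**The case against.** The plan is a pilot and says so. The three-cohort texts disclaim inferential intent and formal sizing, safety is primary, and no subject number was derived from a test. All of that stands: low power is not in itself a fault here. It does not settle the matter, because the SAP still tests every efficacy parameter and grades the p-values in two tiers. A study that disclaims inference has more reason to report estimates.

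Several stronger readings are tempting and the documents do not support them.
- That the SAP reports p-values alone. It also requires counts, percentages, means, SDs, medians and ranges by dose group, so 5/8 and 1/6 would both be visible. What is missing is the between-group difference and its uncertainty. The contents page lists table shells that were not supplied and might show more.
- That the SAP commits the sponsor to reading non-significance as no effect. It labels only p<0.05 and p<0.0167. The presence-or-absence wording is confined to the three-cohort texts, while the SAP's objectives, safety committee and test wording mostly follow the five-cohort text. With title pages removed, the version in force cannot be confirmed.
- That the sufficiency statement is a power claim. It concerns clinical significance for safety and preliminary efficacy, and the next sentence says the size was not set for statistical analysis.
- That carrying over the synopsis's confidence limits would be enough. Those are limits for a group mean, not for a dose-placebo difference.
- That 8 v 6 can detect nothing. Very large effects are within reach, as 0% v 70% shows.

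**Conclusion.** The point holds as a gap in reporting. For each dose against at most 6 pooled placebo subjects, the supplied SAP text gives significance labels and separate group summaries, with no estimate of the difference and no interval. A non-significant result at this size is weak evidence: p<0.05 in Nu-3's favour is unattainable once half of placebo subjects succeed, and with placebo at 20% power is about 20% to 49% for true differences of 40 to 60 points. The five-cohort 8 v 10 comparison raises this only to 30% to 63%.

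The power figures rest on assumed response rates and depend heavily on the placebo rate. The thresholds and the example interval depend only on the group sizes and the counts shown. The conclusion about missing estimates is limited to the supplied text, without table shells. That dose selection would follow the p-values is a risk, not something the documents state.

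**What to change.** In SAP 8.2 and tables 14.2.x, for each dose against pooled placebo:
- binary endpoints: report the difference in proportions with a 95% CI, naming Newcombe or an exact method in advance;
- continuous endpoints: report the Hodges-Lehmann shift with a 95% CI;
- base dose-range statements on these estimates and intervals, and state that a non-significant test is not evidence of no effect.

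If the three-cohort wording in protocol section 7.4 is still in force, reword "each Nu-3 dose group will be compared with placebo to determine the presence or absence of a treatment effect" so that each comparison is made to estimate the treatment effect. No power figure need be written into the protocol, since the sponsor has posited no response rates.

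The cost is a few extra table columns and intervals that openly show low precision. A Newcombe interval will not always agree with Fisher's test: 6/8 v 1/6 gives p=0.10 with limits of about 6 to 81 points. The SAP should therefore say in advance that the interval is there for estimation and is not a second test. No subjects, visits or data are added.

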# **8 RESPONSIBILITIES**

# 8.1 Investigator Responsibilities

### **8.1.1** Good Clinical Practice

The investigator will ensure that this study is conducted in accordance with the principles of the "Declaration of Helsinki" (as amended in Edinburgh, Tokyo, Venice, Hong Kong, and South Africa), International Conference on Harmonization (ICH) guidelines, or with the laws and regulations of the country in which the research is conducted, whichever affords the greater protection to the study subject. For studies conducted under a United States IND, the investigator will ensure that the basic principles of "Good Clinical Practice," as outlined in 21 CFR 312, subpart D, "Responsibilities of Sponsors and Investigators," 21 CFR, part 50, 1998, and 21 CFR, part 56, 1998, are adhered to.

Since this is a "covered" clinical trial, the investigator will ensure that 21 CFR, Part 54, 1998, is adhered to; a "covered" clinical trial is any "study of a drug or device in humans submitted in a marketing application or reclassification petition subject to this part that the applicant or FDA relies on to establish that the product is effective (including studies that show equivalence to an effective product) or that make a significant contribution to the demonstration of safety." This requires that investigators and all sub-investigators must provide documentation of their financial interest or arrangements with Lakewood-Amedex or proprietary interests in the drug being studied. This documentation must be provided before participation of the investigator and any sub-investigator. The investigator and sub-investigator agree to notify Lakewood-Amedex of any change reportable interests during the study and for one year following completion of the study. Study completion is defined as the date that the last subject has completed the protocol defined activities.

This study is also subject to and will be conducted in accordance with 21 CFR, part 320, 1993, "Retention of Bioavailability and Bioequivalence Testing Samples."

# 8.1.2 Institutional Review Board (IRB)/Independent Ethics Committee (IEC) Approval

This protocol and any accompanying material to be provided to the subject (such as advertisements, subject information sheets, or descriptions of the study used to obtain informed consent) will be submitted by the investigator to an IRB in compliance with FDA regulations for IRBs (21CFR Part 56). Approval from the IRB must be obtained **before** starting the study and must be documented in a letter to the investigator specifying the protocol number, protocol version, protocol date, documents reviewed, and date on which the committee met and granted the approval.

Any modifications made to the protocol after receipt of IRB approval must also be submitted to the IRB for approval before implementation.

